#### **Objective 1:**

To evaluate the primary outcome by intervention arm, we will use a linear mixed model to conduct an analysis of covariance (ANCOVA), controlling for site type (ED vs. Urgent Care), index visit pain severity, age, gender, race, medical comorbidities (as the Gagne score), baseline intermittent opioid use, a history of chronic pain, and access to a PCP. These control variables were selected *a priori* based on prior evidence of prognostic value and will not be subjected to significance testing. This model will include all BPI-SF average scores (1, 3, and 6) as outcomes, will include fixed effects for group, time, and group-by-time, as well as all of the control variables, and will use an unstructured covariance matrix for the error terms. We will specify a 6 degrees of freedom (df) linear contrast to test the overall null hypothesis of no mean difference in BPI-SF score at any follow-up visit across the 3 groups at the 5% significance level. If the overall null hypothesis is rejected, we will then conduct separate 3 df contrasts to compare each of the intervention groups with the control group using a Bonferroni-adjusted 2.5% significance level. We will estimate mean pairwise differences along with 95% confidence intervals at each time point. Missing BPI-SF data will be ignored for the primary comparison. The primary analysis will be conducted using the ITT Population, but will also be repeated using the PP Population.

We will also conduct a sensitivity analysis of the primary comparisons using a multiple imputation approach. Pain scores for patients taking analgesics in the past week will be imputed using demographic characteristics, history of chronic pain, pain location, pain etiology (traumatic vs. not traumatic), baseline pain severity, analgesics used, and treatment group.

We will use similar ANCOVA models to test the intervention effects on the secondary outcomes. For continuous or ordinal outcomes, we will use generalized estimating equations models and contrast tests. For any binary variables (e.g., opioid use or non-use) we will also use ANCOVA model but will fit mixed-effect logistic regression models.

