**Figure X****Figure Y****Figure Z**

Thus, we created an exemplary dataset in which participants in the full intervention and video-only groups experienced post-randomization mean pain scores of 20% or 15%, respectively, lower than that in the usual care group. We assumed that loss-to-follow-up times would be exponentially distributed such that the total loss would be 20% at 12 months. Under these assumptions, randomizing 120 participants to each group would provide at least 90% power for testing the overall null hypothesis of no difference across the three groups in mean change from baseline to any follow-up visit through the 6-month visit using linear contrast tested at the 5% significance level (Figure Z).

Furthermore, this sample size would provide about 93% power for the comparison between the full intervention and the usual care group and 67% power for the comparison between the video-only group and the usual care group under these same assumptions, each tested at Bonferroni-adjusted 2.5% significance levels. Because we would like our sample size to support both the intention to treat analysis and the per protocol analysis (restricted to non-admitted patients) and assuming that up to 10% of enrolled patients will be admitted, we plan to enroll 400 patients. The sample size is not calculated based on secondary outcomes. In order to avoid selective reporting of secondary outcomes, we will register and report all secondary outcomes regardless of what is found. The MIXED Procedure in SAS, version 9.4 (SAS Institute, Cary, NC) was used for calculations.

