The Gagne Comorbidity Score will be calculated based on baseline data. The weights indicated below will be applied to each item, as detailed here: <https://scholar.harvard.edu/gagne/software/combined-comorbidity-score> .

```

if disease = 'metastatic_romano' then weight = 5;
if disease = 'chf_romano' then weight = 2;
if disease = 'dementia_romano' then weight = 2;
if disease = 'renal_elixhauser' then weight = 2;
if disease = 'wtloss_elixhauser' then weight = 2;
if disease = 'hemiplegia_romano' then weight = 1;
if disease = 'alcohol_elixhauser' then weight = 1;
if disease = 'tumor_romano' then weight = 1;
if disease = 'arrhythmia_elixhauser' then weight = 1;
if disease = 'pulmonarydz_romano' then weight = 1;

```

```

if disease = 'coagulopathy_elixhauser' then weight = 1;
if disease = 'compdiabetes_elixhauser' then weight = 1;
if disease = 'anemia_elixhauser' then weight = 1;
if disease = 'electrolytes_elixhauser' then weight = 1;
if disease = 'liver_elixhauser' then weight = 1;
if disease = 'pvd_elixhauser' then weight = 1;
if disease = 'psychosis_elixhauser' then weight = 1;
if disease = 'pulmcirc_elixhauser' then weight = 1;
if disease = 'hivaids_romano' then weight = -1;
if disease = 'hypertension_elixhauser' then weight = -1;

```

6. Missing Outcome Data, Out of Window Visits, and Sensitivity Analyses

Missing data for the primary outcome will be ignored (treated as missing at random) in the primary ITT analysis. For the 1-, 3-, and 6-month visits, outcomes for any visits that fall outside the ± 7 day window will be set to missing for the primary analysis (with time computed as follow-up call date minus enrollment date). However, as a first sensitivity analysis, we will repeat the primary analysis using all observed data even if the visits fall outside the visit window. This analysis will repeat the same comparison of mean BPI-SF scores at 30, 90, and 180 days, but time will be treated continuously in this model and actual visit dates will be used. As a second sensitivity analysis, we will repeat the primary analysis using multiple imputation to account for any missing BPI-SF scores. The multivariate normal multiple imputation method will be used, and imputations will be based on all of the control variables included in the primary model.

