comorbidity score, baseline intermittent opioid use, a history of chronic pain, and access to a PCP (access to a PCP was used to stratify the randomization and, as such, it is important to control for it in all models). These control variables were selected a priori based on prior evidence of prognostic value and will not be subjected to significance testing. This model will include all pain severity scores (1, 3, 6, and 12 months) as outcomes; will include fixed effects for group, visit, and group-by-visit; and will use an unstructured covariance matrix for the error terms. We will first test a 6 degrees of freedom (df) linear contrast of the overall null hypothesis of no mean difference in the primary outcome at any of the 1-, 3-, and 6-month follow-up assessments across the 3 groups at the 5% significance level. If the overall null hypothesis is rejected, we will then conduct two separate 3 df contrasts to compare each of the intervention groups with the control group using a Bonferroni-adjusted 2.5% significance level. We will secondarily estimate mean pairwise differences along with 95% confidence intervals at each time point, including data collected at the 12-month follow-up time point.

10. Secondary and Exploratory Analyses (Objective 1)

The same linear mixed modeling approach used for the primary outcome will be applied to each of the separate components of the BPI-SF (Pain Severity and Interference). Similar comparisons using the sequence of linear contrasts and 95% confidence intervals as specified for the primary outcome will be made.

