Similar longitudinal modeling approaches will be applied to evaluate treatment effects on other secondary outcome variables. Appropriate models will be applied depending on the scale of the outcome variable, but the model for fixed effects/linear component will remain consistent across outcomes. For opioid use, a binary outcome, we will apply generalized estimating equations along with a logistic link function and unstructured working covariance matrix. For analgesic-related side effect frequency and severity, physical function, overall health, sleep quality, and healthcare utilization, all quantitative measures, we will compare mean response over time by applying generalized estimating equations along with an identity link function and unstructured working covariance matrix. All comparisons will be made using appropriately specified linear contrasts, tested at the 5% significance level, and/or 95% confidence intervals.

Non-opioid analgesic use and use of other pain management strategies will be descriptively summarized by randomization group and time, without any plans to apply inferential statistical methods (hypothesis tests or confidence intervals).

Exploratory Analyses: To assess whether some groups of participants are more likely to benefit from the interventions, we will estimate and compare effects using tests of interaction for a priori identified subgroups based on gender, race, health literacy, access to a PCP, and preference for control over decision-making⁴. To assess for potentially differential intervention effects on the primary outcome across each of the subgroups, we will use ANCOVA models similar to that for the primary analysis, but with the addition of appropriate interactions between intervention groups and subgroups. Separate models will be used to assess each interaction. Interpretation of differential effects of the intervention will be limited to subgroups for which an interaction is significant at the 5% level.

⁴ After enrollment was converted to remote due to COVID, which meant that the intervention was experienced following the ED visit, the shared decision making items were dropped from the study. Thus, we will not use “preference for control over decision-making” as a variable in our models.

11. Assessing Potential Mechanisms (Objective 2)

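### The PROMIS scores are analysed by GEE with no plan for missed visits; the mixed model already specified for the BPI-SF would remove a small, avoidable bias under missing at random

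*SAP*

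**What the plan says.** SAP section 9 analyses the primary outcome, the combined BPI-SF score, with a linear mixed model that "will use an unstructured covariance matrix for the error terms". Section 10 extends this to severity and interference: "The same linear mixed modeling approach used for the primary outcome will be applied to each of the separate components of the BPI-SF".

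The other quantitative secondary outcomes are side effects, physical function, overall health, sleep quality and healthcare utilization. For these, section 10 changes method: "we will compare mean response over time by applying generalized estimating equations along with an identity link function and unstructured working covariance matrix". They are tested at 5%. The protocol's summary (section 6.1, Objective 1) made the same choice: "For continuous or ordinal outcomes, we will use generalized estimating equations models and contrast tests". The SAP states that it supersedes that summary.

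On missing data, SAP section 6 says "Missing data for the primary outcome will be ignored (treated as missing at random) in the primary ITT analysis", and its sensitivity analysis is equally specific: "we will repeat the primary analysis using multiple imputation to account for any missing BPI-SF scores". For the other scales it covers only missing items within a completed questionnaire. Protocol section 6.1 adds a descriptive comparison of the baseline characteristics of those who did and did not complete follow-up. Neither document says what is assumed or done when a whole visit is missed on a GEE outcome.

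**The concern.** Unweighted GEE is guaranteed consistent only when missingness does not depend on the outcomes, given the covariates in the model. A likelihood-based mixed model with a correct covariance also allows missingness that depends on earlier observed outcomes. The SAP accepts that weaker assumption for pain and uses full maximum likelihood for the mediation models in section 11. It then moves to the more restrictive method for the remaining scales, without stating an assumption for them.

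Participants know their arm (SAP section 4), and the sample size section assumes that "the total loss would be 20% at 12 months". Dropout related to how a participant is doing, and related differently in each arm, is therefore possible, although the documents do not show it. In that case the PROMIS contrasts would carry a bias that the pain contrasts do not.

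**Working it through.** **1. Sample size and loss pattern from the protocol (section 6.2).** 120 × 3 = 360, and 360/(1 − 0.10) = 400, as stated. 400/3 gives about 133 per arm. Exponential loss reaching 20% at 12 months means L(m) = 1 − 0.80^(m/12): 1.8%, 5.4%, 10.6% and 20% at months 1, 3, 6 and 12.

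**2. Why the two methods nearly agree.** With an identity link, both solve Σ Xᵢ′Vᵢ⁻¹(Yᵢ − Xᵢβ) = 0 for the means. They differ only in V. The mixed model estimates V by likelihood from all observed data. GEE estimates it from residual products among those still present, who are a selected group when dropout depends on earlier scores. Some software also forces one scale parameter on all visits, so V is wrong if the spread changes over follow-up.

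**3. Assumptions.** The documents give no SDs, correlations or dropout mechanism for these outcomes. All of the following are assumed: true effect 2 T-score points, and correlation 0.7 between adjacent visits, decaying with distance. Dropout follows logit P(drop) = a + s·z, where z is the standardized previous observed score. s = ±1 is strong dropout and s = ±0.5 moderate, with opposite signs in the two arms. The intercept a is set to give the loss in step 1. Samples are large, with simulation error of about 0.03 points.

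**4. Bias as a share of the true effect.**

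| Scenario | GEE | Mixed model |
|---|---|---|
| Strong dropout, equal SDs or visit-specific variances | about 6–7% at month 12 (0.12–0.14 points) | within about 0.02–0.03 points |
| Strong dropout, SD 6 to 10, one common scale | 0.16, 0.24, 0.06 points at months 3, 6, 12 (8%, 12%, 3%) in one run; peak of 13–15% in another | within about 0.02–0.03 points |
| Same, but correlation 0.7 at every lag | 8%, 14%, 13% at months 3, 6, 12 | – |
| Moderate dropout | 0–8% | essentially unbiased |
| Dropout acts alike in both arms | none | none |

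Reversing the direction of dropout reverses the sign, so an effect can be inflated as well as shrunk.

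**5. How much the unstructured working matrix already does.** In a separate run (no true difference, SD 9, correlations 0.45–0.70, s = ±1), the spurious month-12 difference was 0.23 SD with an independence working matrix and 0.015 SD with the planned unstructured one. The share left is 0.015/0.23 = 7%.

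**6. Against the trial's precision.** With 133 per arm and 20% loss, the standard error of an unadjusted month-12 contrast is √(2/(133 × 0.8)) = 0.137 SD. In 1,000 simulated trials of this size (SD 6 to 10, strong dropout, common scale), root-mean-square error for GEE and mixed model was 0.94 and 0.92 at month 3, 1.17 and 1.15 at month 6, and 1.32 and 1.32 at month 12. The month-6 bias is 0.24/1.15 = 0.21 of a standard error. At the top of the range, 15% of 2 points, it is 0.30/1.15 = 0.26.

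**7. Dropout that depends on the unseen current score.** With s = ±1, the month-12 bias is 0.17 SD for GEE and 0.16 SD for the mixed model.

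**The case against.** A reader might infer that GEE here is valid only if dropout is unrelated to outcomes, so that the secondary results will be materially biased. The documents do not support that. The identity link and unstructured working matrix bring the method close to the mixed model, and dropout explained by model covariates is allowed in any case.

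The larger figures also rest on a single scale parameter. The SAP specifies an unstructured working covariance, which read literally permits visit-specific variances; a common scale is a feature of software, not of the plan. Biases of 15–24% can be produced, but only by spreading the loss evenly over visits, which is not the protocol's exponential pattern.

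Several conditions must hold together: dropout driven by observed scores, acting differently by arm, and, for the upper figures, a rising SD. At this trial's size the two methods have almost the same total error, and the sample size was not set for secondary outcomes. GEE also has a real merit for side-effect scores, which SAP section 5 sets to zero for anyone denying a symptom or taking no pain medication, and for a two-item sleep sum.

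All of this stands and limits the point. What it does not answer is the lack of any stated handling of missed visits, or why the PROMIS T-scores should be treated differently from the BPI-SF components.

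**Conclusion.** The point holds as a modest one. SAP sections 9 and 10 use two methods for similar quantitative scales, and the missing-data plan in section 6 covers the BPI-SF only. Under the protocol's loss pattern and strong, opposite-direction dropout on observed scores, the planned GEE would misstate a 2-point effect by about 6–7% at month 12. At its peak the error would be about 13–15%, if a common scale meets an SD rising from 6 to 10. The mixed model is essentially unbiased in the same cases.

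These sizes depend on assumed SDs, correlations and dropout slopes. A bias of roughly a fifth of a standard error shades an estimate and would rarely change a conclusion. It would also be wrong to infer that the mixed model makes these outcomes safe against all dropout, as step 7 shows. Severity is low to moderate; the case for acting is that the change costs almost nothing.

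**What to change.** In SAP section 10, analyse at least PROMIS Physical Function and PROMIS Global Health with the linear mixed model already specified for the BPI-SF components: unstructured covariance, same fixed effects, same contrasts. State in section 6 that missing at random is assumed for missed visits on these outcomes. Sleep and side-effect scores may use the same model with empirical standard errors, or stay as GEE given their skewed, zero-heavy scales. Opioid use and utilization can stay as GEE. For any quantitative outcome left under GEE, state the missingness assumption and whether variances are visit-specific.

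The cost is SAP wording, since the mixed model has to be programmed for the primary outcome anyway. The downside is a normal-likelihood working model for bounded scores.

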**Objective 2:**

[figure not shown]
[figure not shown]
[figure not shown]
To examine potential mechanisms by which the intervention influences outcomes, we will apply a structural equation model (specifically, a path analysis with manifest variables) with all variables incorporated appropriately for their scale. The model will use data from all patients and will control for demographic and clinical characteristics used for adjusting the Objective 1 model. The primary model will include direct and indirect effects of the interventions on the outcome through potential mediating variables (self-efficacy, use of specific analgesics or behaviors) to allow for assessment of whether mediation is present, and if so, if it is complete or partial. No structural relationship will be imposed relating the mediating variables to one another, beyond simple correlations. We will first test each of the path coefficients from the interventions to the mediator variables separately at the  $p=0.05$  level using chi-squared difference tests. We will then test indirect paths to assess mediation. Standard model fit indices (i.e., RMSEA, Bollen's Incremental Index, and the Tucker-Lewis index) will be reported.

As an exploratory analysis, to assess whether the use of specific medications or recovery promoting behaviors during the first week or the first month mediate pain recovery, these variables will also be examined as potential mediators following the methods described above.

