To address the Objective 2, we will apply structural equation models (specifically, longitudinal path analyses with manifest variables) with all variables incorporated appropriately for their scale. The structural equation models will be fit using MPlus software, version 8.3 or higher. The models will use data from all participants and will control for the same baseline variables as for the primary objective. Full maximum likelihood methods will be used, which allow for inclusion of all observed data for participants who contribute incomplete data. The primary model will include direct and indirect effects from the interventions to the longitudinal outcomes through potential mediating variables (self-efficacy and other “process-related” variables measured at the 1-week phone call) to allow for assessment of whether mediation is present, and if so, whether it is complete or partial. No structural relationships will be imposed relating the potential mediating variables to one another, beyond simple correlations. For the longitudinal outcomes, we will include Pain Severity and Interference in the model as separate variables, which we will allow to be correlated at each time point. We will first test each of the path coefficients from the interventions to the mediator variables separately at the $p=0.05$ level using chi-squared difference tests. We will then test indirect paths to assess mediation. We will compare full and reduced models (with selected paths restricted to be zero) using chi-squared difference tests. Standard model fit indices (i.e., RMSEA, Bollen’s incremental index, and the Tucker-Lewis index) will be reported.

A schematic diagram of the general model set up is shown in Figure 1 below. In this figure, straight arrows represent structural paths, curved arrows represent correlations.

12. Summary of Safety Data

Adverse events will be descriptively summarized for the ITT Population, by randomized treatment group, using frequency tables. Summaries will also be presented according to severity and perceived relatedness to the study. No inferential statistics (hypothesis tests or confidence intervals) will be presented for comparing across groups.

Figure 1. Schematic diagram of the proposed longitudinal path model.

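### SAP Section 11 promises a complete-or-partial mediation verdict but names only tests against zero, so 'complete' could rest only on failing to detect a direct effect

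*SAP*

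**What the plan says.** SAP Section 11 (Objective 2) sets up a longitudinal path model with direct effects of each intervention on the outcomes and indirect effects through mediators measured at the 1-week call. Its stated purpose is "to allow for assessment of whether mediation is present, and if so, whether it is complete or partial". Protocol Section 6.1, Objective 2, has nearly the same wording: "to allow for assessment of whether mediation is present, and if so, if it is complete or partial".

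The SAP lists these steps:

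- "We will first test each of the path coefficients from the interventions to the mediator variables separately". The method is a chi-squared difference test with a 0.05 threshold.
- Indirect paths are tested next, and the finding on mediation rests on them.
- "We will compare full and reduced models (with selected paths restricted to be zero) using chi-squared difference tests".
- Report of three global fit indices, with no thresholds.

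For the outcomes, "we will include Pain Severity and Interference in the model as separate variables".

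Neither document defines complete mediation, sets a margin for a negligible direct effect, asks for a confidence interval on the direct or indirect effects, or gives power for Objective 2. SAP Sections 9 and 10 do ask for 95% intervals on treatment effects; Section 11 does not. The only power figures for the pairwise comparisons are in Protocol Section 6.2 and refer to Objective 1: "93% power for the comparison between the full intervention and the usual care group and 67% power for the comparison between the video-only group".

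**The concern.** Complete mediation is a claim that something is absent: once the mediators are accounted for, the intervention has no remaining effect. A test against zero can show that a direct effect exists. Its failure to reject does not show that the effect is zero or small. That needs an interval narrow enough to exclude effects that matter.

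The comparison with most power for the total effect has less power for any part of it. If half of the benefit is direct, the noncentrality for that half is a quarter of the noncentrality for the whole, other things equal. A direct effect large enough to change the reading of the mechanism can therefore easily be non-significant.

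Objective 2 asks why the interventions do or do not work. A mistaken label of complete mediation would suggest that the 1-week mediators, such as self-efficacy, explain all of the benefit, and would turn attention away from other routes. The risk is also uneven. Video-only has the smaller assumed effect, so its direct path is more likely to be non-significant, and the two arms could appear to work differently for reasons of power alone.

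**Working it through.** **Inputs from the documents**

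- Pairwise power of 93% (full) and 67% (video-only), each at the 2.5% level, with 120 per arm and loss to follow-up already included (Protocol Section 6.2).
- Assumed reductions in mean pain of 20% (full) and 15% (video-only) (Protocol Section 6.2).
- Pairwise contrasts have 3 df, for 1, 3 and 6 months (Protocol Section 6.1; SAP Section 9).
- About 133 per arm planned (Protocol Section 3.3).

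**Assumptions not in the documents**

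- The direct path is tested jointly over three visits (3 df) at 5%.
- The direct effect is the same fraction *f* of the total at each visit.
- It has the same standard error as the total effect.
- The information behind the Objective 1 combined score carries over to the path model.

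**Step 1. Consistency check on the plan's figures.** The means and covariances are in figures not shown, so 93% cannot be rebuilt from raw inputs. Power is P(noncentral chi-squared, 3 df, λ > 9.348), where 9.348 is the 2.5% critical value. Solving for 93% gives λ = 18.09. Scaling to video-only: 18.09 × (15/20)² = 10.18, which gives 67.7% power against the stated 67%. The two figures agree under the 3 df reading. A 1 df reading gives 70.8% and does not fit.

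**Step 2. Noncentrality at the planned size.** Solving from each stated power gives λ = 18.09 (full) and 10.05 (video-only). Multiplying by 133/120 gives 20.05 and 11.14.

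**Step 3. Chance of missing a direct effect.** A share *f* has noncentrality f²λ. The miss rate is P(noncentral chi-squared, 3 df, f²λ ≤ 7.815), where 7.815 is the 5% critical value. For f = 0.5: 20.05/4 = 5.01 and 11.14/4 = 2.79.

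| Direct share of assumed total | Full: missed | Video-only: missed |
|---|---|---|
| 0.25 | 86.6% | 90.6% |
| 0.50 | 55.8% | 74.3% |
| 0.75 | 18.5% | 46.2% |

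**Step 4. Sensitivity for the half-sized direct effect**, 133 per arm, changing one assumption at a time.

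| Change | Full: missed | Video-only: missed |
|---|---|---|
| Base case (3 df, 5%) | 55.8% | 74.3% |
| 2.5% level | 66.6% | 82.6% |
| 6 df, same noncentrality | 66.3% | 80.8% |
| 1 df, noncentrality solved from the powers at 1 df | 50.1% | 70.8% |
| 1 df, same noncentrality as 3 df | 39.0% | 61.4% |
| Direct-path variance × 1.25 from correlation with mediators | 64.1% | 78.9% |
| Mediators remove 20% of residual variance | 46.2% | 68.5% |
| Mediators remove 40% of residual variance | 32.5% | 58.8% |

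These variants span about 32-67% (full) and 59-83% (video-only).

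**Step 5. Size needed.** For 80% power at 3 df and 5%, λ must be 10.90. Per-arm information for the half-sized effect is 18.09/(120 × 4) = 0.0377 (full) and 10.05/(120 × 4) = 0.0209 (video-only). That requires about 290 and 521 per arm, against 133 planned.

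**The case against.** The strongest reply is that the plan never states the rule criticised here. A reader might infer that the SAP has adopted 'non-significant direct path at 5% equals complete mediation'. The documents do not support that. Section 11 speaks of allowing an assessment, the 0.05 level is attached only to the intervention-to-mediator paths, and the direct path is not named among those to be restricted to zero. Direct effects will be estimated in the planned model, and nothing forbids reporting them with intervals. This stands, and it is why the rule is described as implied. It does not remove the gap. A verdict on completeness needs a judgement on the direct path, and tests against zero are the only path-level tools listed. Global fit indices without thresholds cannot supply that judgement.

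A reader might also take 56% and 74% as the error rates of the planned analysis, or as an uncertainty range. They are neither. They are one figure per arm, under one set of assumptions, borrowed from the Objective 1 contrast. The planned model has two correlated outcomes and conditions on mediators, so its df and residual variance will differ. The strength of the mediator-outcome relation is not given in the documents and matters a good deal. In a one-mediator simulation (three visits correlated 0.6, about 119 analysed per arm, total effects 0.50 and 0.37 SD, all assumed), the half-sized direct path was missed in 48% (full) and 69% (video-only) of trials at a slope of 0.4 SD, but in 26% and 54% at 0.6. This stands too: only the wide range is defensible.

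Finally, Objective 2 is secondary. The primary test, its error control and the safety summaries are untouched. That limits the weight of the point.

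**Conclusion.** The point holds as a gap in the plan. Section 11 promises a distinction that its named tools cannot support, because failing to reject a zero direct path does not establish that the path is zero. With the total-effect information implied by Protocol Section 6.2, a direct effect carrying half the assumed benefit would be missed about 56% (full) and 74% (video-only) of the time. Across the df, alpha and residual-variance assumptions tried, the figures are about 32-67% and 59-83%. They rest on the listed assumptions, chiefly the equal standard error and the transfer of Objective 1 information, and the planned model could fall outside them. The exact rates are illustrative. The direction does not depend on them: in no variant tried is the miss rate low enough for non-significance to support a claim of complete mediation. This is a cheap improvement to a secondary objective.

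**What to change.** In SAP Section 11, remove the complete-or-partial verdict. For each intervention, report the direct, indirect and total effects with 95% confidence intervals, for example by bootstrap, from the path model already planned. State that a non-significant direct path will not be read as complete mediation and will be reported as 'direct effect not resolved'. Align the matching sentence in Protocol Section 6.1, or note that the SAP supersedes it.

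A proportion mediated is optional: with two outcomes, several visits and several mediators it yields many ratios, each unstable when the total effect is small. An equivalence margin for the direct effect is also optional. If one is used, it should be justified and fixed before unblinding.

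The cost is a few sentences and some computing, with no new data. The downside is that complete mediation will rarely be claimable at this sample size.
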